3. STUDY OVERVIEW

This is a two-part study to evaluate the PK and safety of EXPAREL in pediatric subjects aged 6 to less than 17 years. Part 1 will evaluate the PK and safety in subjects aged 6 to less than 17 years, while Part 2 will assess the safety in subjects aged 6 to less than 17 years. This is also a two-group study. Group 1 will include subjects aged from 12 to <17 years old undergoing spine surgery. Group 2 will include subjects aged from 6 to <12 years old undergoing spine or cardiac surgery. (Table 1)

In Part 1, subject enrollment will be conducted in parallel to include the older age group (12 to <17 years old; Group 1) and the younger age group (6 to <12 years old; Group 2).

Subject enrollment for Part 2 (of each group) will commence upon completion of Part 1 (of that group). In Part 2, subject enrollment will be conducted in parallel to include the older age group (12 to <17 years old; Group 1) and the younger age group (6 to <12 years old; Group 2).

Dosing of EXPAREL will be based on body weight, with a starting dose of 4 mg/kg (maximum 266 mg). Dosing of Bupivacaine HCl will be based on body weight, with a starting dose of 2 mg/kg (maximum 175 mg).

	Part 1 (PK and Safety)	Part 2 (Safety)
Group 1: subjects aged 12 to <17 years	EXPAREL 4 mg/kg [N=15]; or	EXPAREL 4 mg/kg [N = 15]; or
(Surgery: Spine Surgery)	bupivacaine HCl 2 mg/kg [N =15]	bupivacaine HCl 2 mg/kg [N =15]
Group 2: subjects aged 6 to <12 years (Surgery: Spine or Cardiac Surgery)	EXPAREL 4 mg/kg [N=15]	EXPAREL 4 mg/kg [N =15]

Part 1 (Pharmacokinetics [PK]) - Subjects aged 6 to less than 17 years

Part 1 is a multicenter, randomized, open-label study in 45 subjects aged 6 to less than 17 years of age undergoing spine or cardiac surgeries. Part 1 is divided in 2 groups: Group 1 will include subjects aged 12 to less than 17 years of age, while Group 2 will include subjects aged 6 to less than 12 years of age.

Part 1, Group 1, is an active-controlled, open-labeled, PK evaluation study in subjects aged 12 to less than 17 years undergoing spine surgery. The active comparator will be bupivacaine HCl. The planned sample size for Part 1, Group 1 is 30 subjects (15 subjects per treatment group). Subjects will be randomized 1:1 to receive either a single dose of EXPAREL 4 mg/kg (maximum 266 mg) or bupivacaine HCl 2 mg/kg (not exceeding a maximum bupivacaine HCl dose of 175 mg total) intraoperatively at the end of surgery via local infiltration.

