Part 1, Group 2, is a single arm (EXPAREL 4 mg/kg), open-label, PK evaluation study in subjects aged 6 to less than 12 years undergoing spine or cardiac surgery. The planned sample size for Part 1 Group 2 is 15 subjects. Subjects will receive a single dose of EXPAREL 4 mg/kg (maximum 266 mg) intraoperatively at the end of surgery via local infiltration.

Part 2 (Safety) - Subjects aged 6 to less than 17 years

Part 2 is a multicenter, randomized, open-label study in 45 subjects aged 6 to less than 17 years of age undergoing spine or cardiac surgeries. Part 2 is divided in 2 groups: Group 1 will include subjects aged 12 to less than 17 years of age, while Group 2 will include subjects aged 6 to less than 12 years of age.

Part 2, Group 1, is an active-controlled, open-labeled, safety evaluation study in subjects aged 12 to less than 17 years undergoing spine surgery. The active comparator will be bupivacaine HCl. The planned sample size is 30 subjects (15 subjects per treatment group) for Part 2 Group 1. Subjects will be randomized 1:1 to receive either a single dose of EXPAREL 4 mg/kg (maximum 266 mg) or bupivacaine HCl 2 mg/kg (not exceeding a maximum bupivacaine HCl dose of 175 mg total) intraoperatively at the end of surgery via local infiltration.

Part 2, Group 2, is a single arm (EXPAREL 4 mg/kg), open-label study in subjects aged 6 to less than 12 years undergoing spine or cardiac surgery. The planned sample size for Part 2 Group 2 is 15 subjects. Subjects will receive a single dose of EXPAREL 4 mg/kg (maximum 266 mg) intraoperatively at the end of surgery via local infiltration.

Screening Procedures

Subjects will be screened within 30 days prior to study drug administration. During the screening visit, subjects will be assessed for past or present neurologic, cardiac, and general medical conditions that, in

the opinion of the investigator, would preclude them from study participation. After the Informed Consent Form (ICF) is signed by the subject's legal guardian and written assent is provided by the subject (if capable), medical history, surgical history, physical examination, 12-lead electrocardiogram (ECG), vital sign measurements, neurological assessment, clinical laboratory tests (hematology, chemistry, and urinalysis), pain intensity score assessment, urine pregnancy test (for females of childbearing potential), urine drug screen and alcohol breath test will be conducted.

Study Procedures

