6.7.3 Pharmacokinetic Concentrations and Variables

A complete data listing will be provided for all PK bupivacaine concentration data. Concentrations that are BLOQ will be indicated in the listing.

A plot of bupivacaine concentration-time data, with original scale and semi-log scale overlain on the same page will be created for each individual subject.

If different than the preceding plot, a plot of dose-normalized concentration-time data, with the original scale and semi-log scale overlaid on same page, will also be created for each individual subject.

Plasma bupivacaine concentrations for each formulation will be summarized at each nominal time window (any out-of-window results would be shown only in a listing). The following descriptive statistics

will be presented: n, geometric mean, arithmetic mean, SD, %CV, median, minimum and maximum. Results will be summarized by treatment group (EXPAREL or bupivacaine HCl) for Group 1 and by surgery type (cardiac or spine) for Group 2. Plots of mean bupivacaine concentration over time will be created with the original scale and semi-log scale overlain on the same page. If the number of subjects in a group is less or equal to 3, then individual concentration over time curves will be plotted instead of the mean concentration. For group 1, there will be two plots overlain for the two treatments. For group 2, there will be two separate plots for the two types of surgery.

Pharmacokinetics parameters will be presented in the data listings and descriptive summary statistics, including the arithmetic mean, median, minimum, maximum, standard deviation, %CV of mean, geometric mean, %CV of geometric mean. Differences will be compared between the two formulations using single factor ANOVA.

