Table 14.3-5.1.2: Summary of Incidence of Serious Treatment-Emergent Adverse Events (TEAEs) (Group 2: 6 to < 12 years) - Safety Population

Table 14.3-5.1.3: Summary of Incidence of Serious Treatment-Emergent Adverse Events (TEAEs) (Both Groups: 6 to < 17 years) - Spine Surgery - Safety Population

Note to programmer: Use mock-up 14.3-4.2.1 for the following:

Table 14.3-6.1.1: Summary of Incidence of Treatment-Emergent Adverse Events (TEAEs) of Special Interest (Group 1: 12 to <17 years) - Safety Population

Table 14.3-6.1.2: Summary of Incidence of Treatment-Emergent Adverse Events (TEAEs) of Special Interest (Group 2: 6 to < 12 years) - Safety Population

Table 14.3-6.1.3: Summary of Incidence of Treatment-Emergent Adverse Events (TEAEs) of Special Interest (Both Groups: 6 to < 17 years) - Spine Surgery - Safety Population

Note to programmer: Use mock-up 14.1-5.1.1 for the following:

Table 14.3-7.1.1: Tabulation of Incidence of Prior Medications (Group 1: 12 to <17 years) - Safety Population

Table 14.3-7.1.2: Tabulation of Incidence of Prior Medications (Group 2: 6 to < 12 years) - Safety Population

Note to programmer: On these tables change the footnote 'Intraoperative medications are those indicated as such by the investigator' to read 'Prior medications are those stopped before start of study drug administration.'

Table 14.3-7.1.3: Tabulation of Incidence of Prior Medications (Both Groups: 6 to < 17 years) - Spine Surgery - Safety Population

Table 14.3-8.1.1: Tabulation of Incidence of Concomitant Medications (Group 1: 12 to <17 years) - Safety Population.

Table 14.3-8.1.2: Tabulation of Incidence of Concomitant Medications (Group 2: 6 to < 12 years) - Safety Population.

Note to programmer: On these tables change the footnote 'Intraoperative medications are those indicated as such by the investigator' to read 'Concomitant medications are those taken between the start of study drug administration and discharge from study and are not designated intraoperative medications.' Note that a concomitant medication can start prior to start of study drug and be ongoing.

Table 14.3-8.1.3: Tabulation of Incidence of Concomitant Medications (Both Groups: 6 to < 17 years) - Spine Surgery - Safety Population.

(Page X of Y)

Protocol: 402-C-319

Table 14.4-1.1: Summary of EXPAREL Pharmacokinetic Parameters (Group 1: 12 to <17 years) - PK Population

		EXPAREL	Bupivacaine HCl
	Statistic	[N=xx]	[N=xx]
AUC(0-inf) (hr*ng/mL)	n	XX	XX

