	Mean (%CV)	xx.x (xx.x)	xx.x (xx.x)
	SD	x.xx	X.XX
	Median	XX.X	XX.X
	Geometric Mean (%CV)	XX.X	XX.X
	Minimum, Maximum	XX, XX	XX, XX
	p-value *	0.xxx	
AUC(0-last) (hr*ng/mL)	n	XX	XX
	Mean (%CV)	xx.x (xx.x)	XX.X (XX.X)
	SD	x.xx	X.XX
	Median	XX.X	XX.X
	Geometric Mean (%CV)	XX.X	XX.X
	Minimum, Maximum	XX, XX	XX, XX
	p-value *	0.xxx	

* 2-sided t-test

Source: list SAS datasets used to create table SAS X.Y

ddmmmyyyyThh:mm program name

Note to programmer: Other Pharmacokinetic parameters to appear on this table are, in order of

appearance: Cmax (ng/mL), Tmax, t1/2el (hr), CL/F (L/hr), and Vd (L). Use this template also for tables:

Table 14.4-1.2: Summary of EXPAREL Pharmacokinetic Parameters (Group 2: 6 to < 12 years) - Spine Surgery - PK Population

Table 14.4-1.3: Summary of EXPAREL Pharmacokinetic Parameters (Group 2: 6 to < 12 years) - Cardiac Surgery - PK Population

Table 14.4-1.4: Summary of EXPAREL Pharmacokinetic Parameters (Both Groups: 6 to < 17 years) - Spine Surgery - PK Population

(Page X of Y)

Protocol: 402-C-319

Table 14.4-3.1: Summary of EXPAREL Pharmacokinetic Plasma Concentrations (ng/mL) (Group 1: 12 to <17 years) - PK Population

		EXPAREL	Bupivacaine HCl
	Statistic	[N=XX]	[N=xx]
15 Minutes	n	XX	XX
	Mean (%CV)	xx.x (xx.x)	xx.x (xx.x)
	SD	X.XX	X.XX
	Median	XX.X	XX.X
	Geometric Mean (%CV)	xx.x (xx.x)	xx.x (xx.x)
	Minimum, Maximum	XX, XX	XX, XX
30 Minutes	n	XX	xx
	Mean (%CV)	xx.x (xx.x)	xx.x (xx.x)
	SD	X.XX	X.XX
	Median	XX.X	XX.X
	Geometric Mean (%CV)	xx.x (xx.x)	xx.x (xx.x)
	Minimum, Maximum	XX, XX	XX, XX

Source: list SAS datasets used to create table

ddmmmyyyyThh:mm

SAS X.Y

program name

Note to programmer: Other Pharmacokinetic Plasma Concentration timepoints to appear on this table are, in order of appearance: 45 Minutes, 1 - 1.25 Hours, 2 - 3 Hours, 10 - 18 Hours, 24 - 36 Hours, and 42 - 60 Hours. Use this template also for tables:

Table 14.4-3.2: Summary of EXPAREL Pharmacokinetic Plasma Concentrations (ng/mL) (Group 2: 6 to < 12 years) - Spine Surgery - PK Population

Table 14.4-3.3: Summary of EXPAREL Pharmacokinetic Plasma Concentrations (ng/mL) (Group 2: 6 to < 12 years) - Cardiac Surgery - PK Population

Note to programmer: Change timepoints to: 15 Minutes, 30 Minutes, 45 Minutes, 1 - 1.25 Hours, 15 - 25 Hours, 30 - 40 Hours, 45 - 55 Hours, and 64 - 72 Hours.

Table 14.4-3.4: Summary of EXPAREL Pharmacokinetic Plasma Concentrations (ng/mL) (Both Groups: 6 to < 17 years) - Spine Surgery - PK Population

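### As written, Table 14.4-1.4 would test EXPAREL at 6 to <17 years against bupivacaine HCl at 12 to <17 years, a non-randomised contrast that mainly distorts CL/F and Vd

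*SAP*

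**What the plan says.** SAP section 11 gives one full shell for the noncompartmental PK parameters, "Table 14.4-1.1: Summary of EXPAREL Pharmacokinetic Parameters (Group 1: 12 to <17 years) - PK Population". It has an EXPAREL column and a bupivacaine HCl column. Each parameter shown ends in a p-value row, footnoted as a two-sided t-test. The programmer note then lists the remaining parameters and the reuse: "Cmax (ng/mL), Tmax, t1/2el (hr), CL/F (L/hr), and Vd (L). Use this template also for tables". The tables named are 14.4-1.2 (Group 2 spine), 14.4-1.3 (Group 2 cardiac) and "Table 14.4-1.4: Summary of EXPAREL Pharmacokinetic Parameters (Both Groups: 6 to < 17 years) - Spine Surgery - PK Population". No note changes the columns or removes the p-value for any of the three.

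The arms are set out in SAP section 3. For Group 1, "Subjects will be randomized 1:1 to receive either a single dose of EXPAREL 4 mg/kg (maximum 266 mg) or bupivacaine HCl 2 mg/kg", and "The planned sample size for Part 1, Group 1 is 30 subjects (15 subjects per treatment group"); all have spine surgery. For the younger children, "Part 1, Group 2, is a single arm (EXPAREL 4 mg/kg), open-label, PK evaluation study in subjects aged 6 to less than 12 years", with 15 planned and spine or cardiac surgery allowed.

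SAP 6.7.3 describes the test: "Differences will be compared between the two formulations using single factor ANOVA". It names no covariate and no restriction to Group 1. SAP 6.7.2 defines CL/F as dose over AUC0-∞ and Vd/F as dose over the product of λz and AUC0-∞. Neither is divided by weight.

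**The concern.** In Table 14.4-1.4 the younger children can enter only the EXPAREL column, because no child under 12 is assigned bupivacaine HCl. The p-value would therefore compare a mixed-age EXPAREL group with a comparator aged 12 to <17. Randomisation does not protect that comparison.

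CL/F in L/hr and Vd in L are smaller in smaller children whatever the formulation. A difference caused by age and weight could be read as a formulation effect. Both columns can be filled and the test will compute, so nothing in the output would flag the problem.

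**Working it through.** The plan states no alpha, effect size or variability for this test, so it has no figure of its own to reproduce.

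**Who fills each column.** Let k be the number of Group 2 Part 1 children having spine surgery. The SAP plans 15 Group 2 children and gives no spine/cardiac split, so k is 0 to 15. EXPAREL column: 15 + k, which is 15 to 30. Bupivacaine HCl column: 15, all aged 12 to <17.

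**Which test.** For two groups, single-factor ANOVA and the two-sided pooled t-test give the same p-value, so SAP 6.7.3 and the shell describe one test.

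**Shift in mean EXPAREL CL/F from size alone.** Assume clearance is proportional to weight^b, with no formulation difference at a given weight. Let r = (mean weight at 6 to <12 / mean weight at 12 to <17)^b. Then

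relative fall = k/(15 + k) × (1 − r).

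The fraction is 0 for k = 0, 5/20 = 0.25 for k = 5 and 15/30 = 0.50 for k = 15. The weights and exponents below are assumptions; the documents give none.

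| Mean weights (kg) | b | r | k = 5 | k = 15 |
|---|---|---|---|---|
| 25 / 50 | 1 | 0.500 | 12.5% | 25.0% |
| 25 / 50 | 0.75 | 0.595 | 10.1% | 20.3% |
| 30 / 52 | 1 | 0.577 | 10.6% | 21.2% |
| 30 / 52 | 0.75 | 0.662 | 8.5% | 16.9% |
| 35 / 55 | 1 | 0.636 | 9.1% | 18.2% |
| 35 / 55 | 0.75 | 0.712 | 7.2% | 14.4% |
| 35 / 50 | 1 | 0.700 | 7.5% | 15.0% |
| 35 / 50 | 0.75 | 0.765 | 5.9% | 11.7% |

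**Vd.** By the SAP's formulas Vd/F = (CL/F)/λz. If volume is proportional to weight, the b = 1 rows apply. If slow release governs EXPAREL's terminal slope, Vd/F scales as CL/F does. Either way the fall lies in the same range.

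**AUC.** Dose is per kg up to the caps, reached at 266/4 = 66.5 kg for EXPAREL and 175/2 = 87.5 kg for bupivacaine HCl. Below the caps, AUC is proportional to weight^(1 − b). With b = 1 there is no shift. With b = 0.75 and 25/50 kg, 0.5^0.25 = 0.841, so the fall is 0.25 × 0.159 = 4.0% for k = 5 and 0.50 × 0.159 = 8.0% for k = 15. The nominal dose ratio is 4/2 = 2, so it dominates the raw AUC contrast. Cmax was not calculated separately; the same per-kg reasoning applies.

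**Effect on the p-value.** This was simulated with 20,000 runs per scenario. Further assumptions were weight CV 20%, clearance CV 30% or 50%, nominal alpha 0.05 and no true difference in size-adjusted clearance. The first three weight pairs above were used.

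- CL/F in L/hr, pooled: rejection in 6.6-13.7% of runs with k = 5 and 15.6-54.4% with k = 15.
- CL/F in L/hr, k = 0 (15 vs 15, same ages; 30/52 kg only): 4.6-4.9%.
- CL/F per kg, pooled: 4.4-5.1% if b = 1, but 4.6-12.4% if b = 0.75.
- Raw AUC at 4 vs 2 mg/kg: EXPAREL to bupivacaine HCl ratio about 1.8-2.0.

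**The case against.** The strongest reply is that the shells are shorthand. The same note sends the template to Tables 14.4-1.2 and 14.4-1.3, where no bupivacaine HCl arm exists and neither the column nor the p-value can be filled. At least two of the three reuses must therefore be adapted. Another note asks for spine and cardiac columns in Table 14.3-2.1.3, which is spine-only. The two formulations coexist only in Group 1, and SAP 6.1 presents Group 1 by treatment and Group 2 by surgery type. The sponsor may well have meant EXPAREL-only tables.

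This makes the intent uncertain, but it does not settle Table 14.4-1.4. The EXPAREL title does not help, since Table 14.4-1.1 carries the same title and has a comparator column. Column and timepoint changes are written out elsewhere, for example for Table 14.4-3.3. SAP 6.9.2.1 expressly confines its log-rank p-value to Group 1, and SAP 6.7.3 has no such limit.

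Three further points stand:

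- The size rests on assumed weights and on an unstated k. With k = 0, Table 14.4-1.4 equals Table 14.4-1.1.
- Not every child may yield CL/F or Vd/F, because λz needs three points after Cmax. The groups may be smaller than 15 + k and 15.
- The consequence is limited. Protocol sections 15.1 and 15.7 plan no significance testing, population PK is the protocol's PK method, and SAP 6.11 presents the noncompartmental analysis as an addition.

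A reader might infer that every p-value in the table would partly or wholly reflect age and weight. The documents do not support that. AUC and Cmax are driven mainly by the twofold dose difference, and for AUC the size shift pulls EXPAREL towards the comparator.

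**Conclusion.** The point holds on the SAP's literal wording, as a minor defect in one shell. The note, unamended, yields a computable p-value for a comparison that is confounded by age and is not randomised. It matters mainly for CL/F in L/hr and Vd in L.

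Under the stated assumptions the fall in mean EXPAREL CL/F is zero with no Group 2 spine children and roughly 6-13% with 5. With 15 it is roughly 14-25%, or about 12% at the closest weight pair tried. These figures rest on assumed mean weights of 25-35 and 50-55 kg and exponents of 0.75 to 1, so they show a range and do not predict a result.

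Two stronger conclusions are not supported. The documents do not show that the sponsor intends a pooled formulation test. Nor does the defect undermine the primary PK characterisation: the randomised comparison is already in Table 14.4-1.1.

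**What to change.** In the programmer note after Table 14.4-1.1:

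- Make Table 14.4-1.4 EXPAREL-only, with columns for 12 to <17 years, 6 to <12 years and total, no bupivacaine HCl column and no p-value.
- Drop the comparator column and the p-value row from Tables 14.4-1.2 and 14.4-1.3 as well.

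In SAP 6.7.3, limit the formulation comparison to Group 1, as reported in Table 14.4-1.1.

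Weight-normalised CL/F and Vd/F rows (L/hr/kg and L/kg) are an optional descriptive addition, using the weight already collected under SAP 6.3.2. They do not replace removal of the pooled p-value, because per-kg scaling still left rejection as high as 12.4% when b = 0.75.

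The cost is a few lines of SAP text. No new data are needed, and the randomised comparison is kept.

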ddmmmyyyyThh:mm program_name

(Page X of Y)

Protocol: 402-C-319

Listing 16.2-2.1.1: Randomization and Populations (Group 1: 12 to <17 years) - All Subjects

			Randomization		Population	
Site	Subject	Part	Date and Time	Number	Safety	PK
XXX	VVVV	Part 1	ddmmmyyyyThh:mm	XXXXX	X	x

Part 2

Source: list SAS datasets used to create table SAS X.Y

ddmmmyyyyThh:mm program name

Note to programmer: Population will by 'Y' if subject in set, blank otherwise. Use this template also for listing:

Listing 16.2-2.1.2: Enrollment and Populations (Group 2: 6 to < 12 years) - All Subjects

Note to programmer: Change "Randomization" column header to "Enrollment".

(Page X of Y)

Protocol: 402-C-319

Listing 16.2-3.1.1: Demographics (Group 1: 12 to <17 years) - All Subjects

TREATME	NT: treatme	ent-name						
	Subject							
Site	Number	Init.	Birth Date	Age(yrs)	Sex	Race	Ethnicity	ASA Class
XXX	УУУУ	AMZ	ddmmmyyyy	XX	Х	XXXXXXXXXXX	XXXXXXXXX	Х

The following subjects were not placed in the correct group according to their age: xxxx, xxxx, .

Source: list SAS datasets used to create table

 ${\tt ddmmmyyyyThh:} {\tt mm}$

program name

SAS X.Y

Note to programmer: If race is 'other' then race should be 'Other: other-specify-text'. Use this template also for listing:

Listing 16.2-3.1.2: Demographics (Group 2: 6 to < 12 years) - All Subjects

SAS X.Y

Note to programmer: Use this template also for listing:

Listing 16.2-4.1.2: Height and Weight (Group 2: 6 to < 12 years) - All Subjects

Pacira Pharmaceuticals

Listing 16.2-4.1.1: Height and Weight (Group 1: 12 to <17 years) - All Subjects

Site	Subject	Collection Date	Height (cm)	Weight (kg)	Body Mass Index (kg/m²)
XXX	УУУУ	ddmmmyyyyThh:mm	xxx.X	xxx.X	xx.X

Source: list SAS datasets used to create table

ddmmmyyyyThh:mm

program name

(Page X of Y)

Protocol: 402-C-319

Pacira Pharmaceuticals	(Page X of Y)
------------------------	---------------

Protocol: 402-C-319

Listing 16.2-5.1.1: Surgery (Group 1: 12 to <17 years) - All Subjects

Start Stop Duration Procedure Length Medic	and the state of the second
	cations
Site Subject Date Time Time (hrs) Name (cm) Admini	istered?

Source: list SAS datasets used to create table SAS X.Y

ddmmmyyyyThh:mm program name

Note to programmer: If anesthesia type is 'other' then text should read 'other: specify-text'. Procedure Name is 'Cardiac' or 'Spine'. Use this template also for listing:

Listing 16.2-5.1.2: Surgery (Group 2: 6 to < 12 years) - All Subjects

(Page X of Y)

Protocol: 402-C-319

Listing 16.2-6.1.1: Numeric Rating Scale at Rest Pain Intensity Score (Group 1: 12 to <17 years) - All Subjects

			Ti	Time From Dose				
Site	Subject	Date and Time	Scheduled(hr)	Actual(hr)	Deviation(hrs)	Pain Score		
xxx	УУУУ	ddmmmyyyyThh:mm	XX.XX	xx.xx	XXXX	XX.X		
		ddmmmyyyyThh:mm	Day 1 Pre-op	XX.XX	XXXX	XX.X		
		ddmmmyyyyThh:mm *	4 hours	XX.XX	XXXX	XX.X		
		ND	8 hours					
		ddmmmyyyyThh:mm	12 hours	XX.XX	XXXX	XX.X		
		ddmmmyyyyThh:mm	Unscheduled	XX.XX	XXXX	XX.X		
		ddmmmyyyyThh:mm		XX.XX	XXXX	XX.X		
		ddmmmyyyyThh:mm	Hospital discharge	XX.XX	XXXX	XX.X		

ND=Not Done; * = out of window Source: *list SAS datasets used to create table* SAS X.Y

ddmmmyyyyThh:mm program name

Note to programmer: Sort by collection date and time. If Pain Intensity Score was taken due to rescue medication dosing, put RESCUE in scheduled column and hours from dose in actual column - leave deviation column blank. Do not split a subject's data across pages if it can be avoided. An asterisk (*) will be placed next to the deviation if an assessment is out of window. See Table of Time and Events for windows. Use this template also for listing:

Listing 16.2-6.1.2: Color Analog Scale Pain Intensity Score (Group 2: 6 to < 12 years) - All Subjects

EXPAREL®		Statistical Analysis Plan
Pacira Pharmaceuticals	(Page X of Y)	Protocol: 402-C-319
Listing 16.2-7.1.1.1: Opioid Medication To years) - All Subjects	otal Dose (MED mg) and Opioid-free Status	(Group 1: 12 to <17

TREATM	ENT: treatment-r	name			
Site	Subject	0-24 hrs [1]	0-48 hrs [1]	0-72 hrs [1]	Opioid-Free
XXX	УУУУ	XXXX.X	XXXX.X	XXXX.X	NO
XXX	УУУУ	-	-	-	YES

Total dose is dose from end of surgery through timepoint.	
[1] Time 0 is defined as the time of the end of surgery.	
Source: list SAS datasets used to create table	ddmmmyyyyThh:mm
SAS X.Y	program_name

Note to programmer: Use this template also for listing:

Listing 16.2-7.1.1.2: Opioid Medication Total Dose (MED mg) and Opioid-free Status (Group 2: 6 to < 12 years) - All Subjects

(Page X of Y)

Protocol: 402-C-319

Listing 16.2-7.2.1.1: Opioid Medication (Group 1: 12 to <17 years) - All Subjects

TREAT	REATMENT: treatment-name											
			Time to		Dose	Conversion	Dose (MED					
Site	Subject	Date and Time	Rescue (hr)	Medication	(units)	Factor	mg)	Route				
XXX	УУУУ	ddmmmyyyyThh:mm ddmmmyyyyThh:mm ddmmmyyyyThh:mm ddmmmyyyyThh:mm	xxx.x xxx.x xxx.x xxx.x	xxxxxxxxxxxxx xxxxxxxxxxx xxxxxxxxxxxx	xx (xxxx) xx (xxxx) xx (xxxx) xx (xxxx)	x.xx x.xx x.xx x.xx	xxx.x xxx.x xxx.x xxx.x	xxxxxxx xxxxxxx xxxxxxx xxxxxxx				

Time to rescue is time from end of surgery to rescue medication dose. Source: *list SAS datasets used to create table* SAS X.Y

ddmmmyyyyThh:mm program name

Note to programmer: Medication should be preferred term. If medication or route is 'Other', text should read 'Other: specify-text'. Sort by date and time within subject. Use this template also for listing:

Listing 16.2-7.2.1.2: Opioid Medication (Group 2: 6 to < 12 years) - All Subjects

Pacira Pharmaceuticals, Inc.

EXPAREL[®]

Listing 16.2-8.1.1: Day 7 Phone Call (Group 1: 12 to <17 years) - All Subjects

TREATMENT:	treatment-name

			Day 7 Phone Call		related				
Site	Subject	Date	Schedule (days)	Actual (days)	Deviation (days)	Phone Calls	Office Visits	Number of ER Visits	AE Assessed
			_						
XXX	YYYY	DDMONYYYY	/	XX.X	XX.X	XX	XX	XXXX	Yes
XXX	YYYY	DDMONYYYY	7	XX.X	XX.X	XX	XX	XXXX	No
XXX	YYYY	DDMONYYYY	7	XX.X	XX.X	XX	XX	XXXX	No

ER = Emergency Department

Source: list SAS datasets used to create table

DDMONYYYYTHH:MM

SAS X.Y

Note to programmer: Sort by date and time within subject. Use this template also for listing:

Listing 16.2-8.1.2: Day 7 Phone Call (Group 2: 6 to < 12 years) - All Subjects

Note to programmer: Replace treatment columns by Spine Surgery and Cardiac Surgery for this table.

Listing 16.2-8.1.3: Day 30 Visit (Group 1: 12 to <17 years) - All Subjects Note to programmer: Change "Day 7 Phone Call" column to "Day 30 Visit".

Listing 16.2-8.1.4: Day 30 Visit (Group 2: 6 to < 12 years) - All Subjects

Note to programmer: Change "Day 7 Phone Call" column to "Day 30 Visit". Replace treatment columns by Spine Surgery and Cardiac Surgery for this table.

Protocol: 402-C-319

(Page X of Y)

(Page X of Y)

Protocol: 402-C-319

Listing 16.2-9.1.1.1: EXPAREL Pharmacokinetic Concentrations (Raw) (Group 1: 12 to <17 years) - All Subjects

		Scheduled Timepoint		Actual	Deviation	Concentration Original
Site	Subject	(hrs)	Date and Time	(hrs)	(hrs)	(ng/mL)
XXX	УУУУ	XX	yyyy-MM-DDThh:mm	_	_	XXXX.X
		XX	yyyy-MM-DDThh:mm	XX.X	XX.X	XXXX.X
		XX	yyyy-MM-DDThh:mm	XX.X	XX.X	xxxx.x
		XX-XX	yyyy-MM-DDThh:mm	XX.X	XX.X	XXXX.X
		XX-XX	yyyy-MM-DDThh:mm	XX.X	XX.X	XXXX.X
		XX-XX	yyyy-MM-DDThh:mm	XX.X	XX.X	XXXX.X
		XX-XX	yyyy-MM-DDThh:mm	XX.X	XX.X	XXXX.X
		XX-XX	yyyy-MM-DDThh:mm	XX.X	XX.X	XXXX.X

BLOQ = Below limit of quantification. ND = Not determined.

Source: list SAS datasets used to create table

SAS X.Y

ddmmmyyyyThh:mm

program name

Note to programmer: Scheduled time points are different for spine and cardiac surgeries. Sort by date and time within subject. Use this template also for listings:

Listing 16.2-9.1.1.2: EXPAREL Pharmacokinetic Concentrations (Raw) (Group 2: 6 to < 12 years) - Spine Surgery - All Subjects

Listing 16.2-9.1.1.3: EXPAREL Pharmacokinetic Concentrations (Raw) (Group 2: 6 to < 12 years) - Cardiac Surgery - All Subjects

Listing 16.2-9.3.1.1: Bupivacaine Pharmacokinetic Concentrations (Raw) (Group 1: 12 to <17 years) - All Subjects

Pacira Pharmaceuticals(Page X of Y)Protocol: 402-C-319

Listing 16.2-9.5.1.1: EXPAREL Pharmacokinetic Parameters (Group 1: 12 to <17 years) - PK Population

Site	Subject	AUC(0-inf) (ng*hr/mL)	AUC(0-last) (ng*hr/mL)	Cmax (ng/mL)	Tmax	t1/2el (hr)	CL/F (L/hr)	Vd (L)
XXX	УУУУ	XXXX.XX	XXXX.XX	XXX.X	Χ.ΧΧ	Χ.ΧΧ	XX.XX	XX.XX

ND = Not determined.Source: list SAS datasets used to create tableddmmmyyyyThh:mmSAS X.Yprogram name

Note to programmer: Sort by site and subject. Use this template also for listings:

Listing 16.2-9.5.1.2: EXPAREL Pharmacokinetic Parameters (Group 2: 6 to < 12 years) - Spine Surgery - PK Population

Listing 16.2-9.5.1.3: EXPAREL Pharmacokinetic Parameters (Group 2: 6 to < 12 years) - Cardiac Surgery - PK Population

Listing 16.2-9.6.1.1: Bupivacaine Pharmacokinetic Parameters (Group 1: 12 to <17 years) - PK Population

Pacira Pharmaceuticals, Inc. EXPAREL[®]

Pacira Pharmaceuticals

(Page X of Y)

Protocol: 402-C-319

Listing 16.2-10.1.1: Hematology (Group 1: 12 to <17 years) - All Subjects

TREATMEN	NT: treatmen	it-name							
			Analyte (units)		Normal	Range	_		
Subject	Visit	Date and Time			Low	High	Result	Change	Flag
УУУУ	Screening	ddmmmyyyyThh:mm	XXXXXXXXXXXXX	(units)	XXX.XX	XXX.XX	XXX.XX	-	Н
			******	(units)	XXX.XX	xxx.xx	xxx.xx	-	
			Xxxxxxxxxxx	(units)	XXX.XX	xxx.xx	xxx.xx	-	L
			Xxxxxxxxxxx	(units)	XXX.XX	xxx.xx	xxx.xx	-	
	Baseline	ddmmmyyyyThh:mm	Xxxxxxxxxxx	(units)	XXX.XX	xxx.xx	xxx.xx	_	
			Xxxxxxxxxxx	(units)	XXX.XX	XXX.XX	XXX.XX	_	
			Xxxxxxxxxxx	(units)	XXX.XX	xxx.xx	XXX.XX	-	L
			Xxxxxxxxxxx	(units)	XXX.XX	xxx.xx	xxx.xx	-	
	96 Hours	ddmmmyyyyThh:mm	*****	(units)	xxx.xx	xxx.xx	xxx.xx	xx.X	
			*****	(units)	XXX.XX	xxx.xx	xxx.xx	xx.X	
			*****	(units)	XXX.XX	xxx.xx	xxx.xx	xx.X	L
			******	(units)	XXX.XX	xxx.xx	XXX.XX	xx.X	

Flag: L=below normal range; H=above normal range.

Source: list SAS datasets used to create table

ddmmmyyyyThh:mm

SAS X.Y

program name

Note to programmer: Sort by date and time within subject and analyte alphabetically within date. Change is only calculated for Day 10 visit. Use this template also for listings:

Listing 16.2-10.1.2: Hematology (Group 2: 6 to < 12 years) - All Subjects

Note to programmer: Replace "TREATMENT" with "SURGERY TYPE", followed by "Spine Surgery" or "Cardiac Surgery".

Listing 16.2-11.1.1: Chemistry (Group 1: 12 to <17 years) - All Subjects

Listing 16.2-11.1.2: Chemistry (Group 2: 6 to < 12 years) - All Subjects

Note to programmer: Replace "TREATMENT" with "SURGERY TYPE", followed by "Spine Surgery" or "Cardiac Surgery".

Listing 16.2-12.1.1: Urinalysis - Numeric Results (Group 1: 12 to <17 years) - All Subjects

Listing 16.2-12.1.2: Urinalysis - Numeric Results (Group 2: 6 to < 12 years) - All Subjects

(Page X of Y)

Protocol: 402-C-319

Listing 16.2-13.1.1: Urinalysis - Character Results (Group 1: 12 to <17 years) - All Subjects

TREAT	MENT: treat	ment-name					
Site	Subject	Visit	Date and Time	Analyte	Normal Criteria	Result	Flag
XXX	УУУУ	Screening	ddmmmyyyyThh:mm	xxxxxxxxxxxxXX xxxxxxxxxxXXX 	xxxxxxx xxxxxxxx	xxxxxxxx xxxxxxxx	A
		Baseline	ddmmmyyyyThh:mm	xxxxxxxxxxxxXX xxxxxxxxxxXXX 	xxxxxxx xxxxxxxx	xxxxxxxx xxxxxxxx	A
		Day 10	ddmmmyyyyThh:mm	xxxxxxxxxxxxxXXX xxxxxxxxxxXXXXXXXXXXX	xxxxxxxx xxxxxxxx	xxxxxxxx xxxxxxxx	

Flag: A = abnormal.

Source: list SAS datasets used to create table

ddmmmyyyyThh:mm

SAS X.Y

program name

Note to programmer: Sort by date and time within subject and analyte alphabetically within date. Use this template also for listing:

Listing 16.2-13.1.2: Urinalysis - Character Results (Group 2: 6 to < 12 years) - All Subjects

Pacira Pharmaceuticals, Inc. EXPAREL[®]

Pacira Pharmaceuticals

(Page X of Y)

Protocol: 402-C-319

Listing 16.2-14.1.1: Vital Signs Assessment (Group 1: 12 to <17 years) - All Subjects

TREATMENT: treatment-name

						Heart Rate	Temp.	SBP	DBP	Respirat ory rate (breaths	Oxygen
			Assessment			(bpm)	(°C)	(mmHq)	(mmHq)	(bieachs /min)	Sat. (%)
			Schedule	Actual	Dev.	Actual	Actual	Actual	Actual	Actual	Actual
Site	Subject	Date and Time	(hrs)	(hrs)	(hrs)	(Change)	(Change)	(Change)	(Change)	(Change)	(Change)
XXX	УУУУ	ddmmmyyyyThh:mm	Screening	_	-	XX	XX	XXX	XX	XX	XX
		ddmmmyyyyThh:mm	Baseline	-	-	XX	XX	XXX	XX	XX	XX
		ddmmmyyyyThh:mm	2	xxx.xx	XXX	XX	XX	XXX	XX	XX	XX
						(-xx)	(-xx)	(-xx)	(-xx)	(-xx)	(-xx)
		ddmmmyyyyThh:mm	4	xxx.xx	XXX	XX	XX	XXX	XX	XX	XX
						(xx)	(xx)	(xx)	(XX)	(xx)	(xx)
		ddmmmyyyyThh:mm	8	xxx.xx	XXX	XX	XX	XXX	XX	XX	XX
						(xx)	(xx)	(xx)	(XX)	(xx)	(xx)
		ddmmmyyyyThh:mm	12	xxx.xx	XXX	xx H	XX H	XXX	XX	XX	XX
						(xx)	(xx)	(xx)	(XX)	(xx)	(xx)
		ddmmmyyyyThh:mm	24	XXX.XX	XXX	XX LI	XX LI	XXX	XX	XX	XX
						(xx)	(xx)	(xx)	(XX)	(xx)	(XX)
		ddmmmyyyyThh:mm	36	xxx.xx	XXX	XX	XX	XXX	XX	XX	XX
						(xx)	(xx)	(xx)	(XX)	(xx)	(XX)
		ddmmmyyyyThh:mm	48	XXX.XX	XXX	XX	XX	XXX	XX	XX	XX
						(xx)	(xx)	(xx)	(XX)	(xx)	(xx)
		ddmmmyyyyThh:mm	60	xxx.xx	XXX	XX	XX	XXX	XX	XX	XX
						(xx)	(xx)	(xx)	(XX)	(xx)	(xx)
		ddmmmyyyyThh:mm	72	XXX.XX	XXX	XX	XX	XXX	XX	XX	XX
						(xx)	(xx)	(xx)	(XX)	(xx)	(xx)
		ddmmmyyyyThh:mm	96	XXX.XX	XXX	XX	XX	XXX	XX	XX	XX
						(xx)	(xx)	(xx)	(XX)	(xx)	(xx)
			Hospital								
		ddmmmyyyyThh:mm	Discharge	XXX.XX	XXX	XX	XX	XXX	XX	XX	XX
						(xx)	(xx)	(xx)	(XX)	(xx)	(XX)
		ddmmmyyyyThh:mm	Day 30	XXX.XX	XXX	XX	XX	XXX	XX	XX	XX
						(XX)	(xx)	(xx)	(XX)	(XX)	(XX)

*=out of window; Change is change from baseline. Source: *list SAS datasets used to create table* SAS X.Y

ddmmmyyyyThh:mm program_name **Note to programmer:** Sort by date and time within subject. An asterisk (*) will be placed next to the deviation if an assessment is out of window. See Table of Time and Events for windows. Use this template also for listing:

Listing 16.2-14.1.2: Vital Signs Assessment (Group 2: 6 to < 12 years) - All Subjects

(Page X of Y)

Protocol: 402-C-319

Listing 16.2-15-1.1: Electrocardiogram Findings - Investigator Assessment (Group 1: 12 to <17 years) - All Subjects

TREAT	MENT: treat	ment-name		
			Assessment	
	-		Schedule	_
Site	Subject	Date and Time	(hrs)	Finding
XXX	УУУУ	ddmmmyyyyThh:mm	Screening	Normal

*=out of window

Source:	list	SAS	datasets	used	to	create	table	
SAS X.Y								

ddmmmyyyyThh:mm program name

Note to programmer: Sort by date and time within subject. Use this template also for listing:

Listing 16.2-15-1.2: Electrocardiogram Findings - Investigator Assessment (Group 2: 6 to < 12 years) - All Subjects

(Page X of Y)

Protocol: 402-C-319

Listing 16.2-16.1.1: Neurological Assessment (Group 1: 12 to <17 years) - All Subjects

TREATMENT: treatment-name Assessment Question Schedule Actual Deviation (hrs) (hrs) 5 Site Subject Date and Time (hrs) 1 2 3 4 6 ddmmmyyyyThh:mm Screening _ _ Х Х XXX YYYY Х Х Х Х ddmmmvvvvThh:mm 2 Х Х Х Х XXX.XX XXX NA Х 4 ddmmmvvvvThh:mm Х Х Х XXX.XX XXX Х Х Х ddmmmvvvvThh:mm 8 Х Х Х Х Х Х XXX.XX XXX ddmmmyyyyThh:mm 12 Х Х XXX.XX XXX NA Х Х Х ddmmmyyyyThh:mm 24 Х XXX.XX XXX Х Х Х Х Х ddmmmyyyyThh:mm 36 Х Х Х Х XXX.XX XXX Х Х ddmmmyyyyThh:mm 48 XXX.XX XXX Х Х Х Х Х Х ddmmmyyyyThh:mm 60 Х Х Х Х Х XXX.XX XXX Х ddmmmyyyyThh:mm 72 Х Х Х Х Х Х XXX.XX XXX ddmmmvvvvThh:mm 96 XXX.XX Х Х Х Х Х Х XXX Hospital ddmmmvvvvThh:mm Discharge _ Х Х Х Х Х Х XXX.XX ddmmmvvvvThh:mm Day 30 XXX.XX Х Х Х Х Х Х XXX

*=out of window; NA=Not Assessable

Is subject oriented?
 Do you have numbress of the lips, the tongue or around the mouth?
 Do you have a metallic taste in your mouth?
 Are you having problems with your hearing not related to the use of a hearing aid?
 Are your having problems with your vision not related to the use of eye glasses?
 Are your muscles twitching?
 Source: list SAS datasets used to create table
 SAS X.Y

Note to programmer: Sort by date and time within subject. An asterisk (*) will be placed next to the deviation if an assessment is out of window. See Table of Time and Events for windows. Use this template also for listing:

Listing 16.2-16.1.2: Neurological Assessment (Group 2: 6 to < 12 years) - All Subjects

(Page X of Y)

Protocol: 402-C-319

Listing 16.2-17.1.1.1: All Adverse Events (Group 1: 12 to <17 years) - All Subjects

Treat	ment: trea	atment-	name	
Site	Subject	TEAE	Data Type	Data
XXX	УУУУ	N	Start (Day)	ddmmmyyyyThh:mm (XX)
			Stop (Day)	ddmmmyyyyThh:mm (XX)
			AE Number	X
			System Organ Class	XXXXXXXXXXXXXXXXX
		Preferred	*****	
		Verbatim	XXXXXXXXXXXXXXXXXXXXXXXXXXXXXXXXXXXXXXX	
			Severity	XXXXXXX
			Relationship to Study	XXXXXXX
			Drug	
			Action Taken	*****
			Outcome	XXXXXXXXXXXXX
			Serious	XXX
			Serious Cause(s)	XXXXXXXXXXXXX
				XXXXXXXXXXXXXXXXXXXXXXXXXXXXXXXXXXXXXXX

TEAE: Treatment-emergent AE (Y=TEAE/N=Not TEAE)

Source: list SAS datasets used to create listing SAS X.Y

ddmmmyyyyThh:mm

program name

Note to programmer: If AE is ongoing, put ONGOING in stop row. Do not split an AE across pages. Insert a page break between subjects. Use this template also for listings:

Listing 16.2-17.1.1.2: All Adverse Events (Group 2: 6 to < 12 years) - All Subjects

Note to programmer: Replace "TREATMENT" with "SURGERY TYPE", followed by "Spine Surgery" or "Cardiac Surgery".

Listing 16.2-17.2.1.1.1: Treatment-emergent Adverse Events (Group 1: 12 to <17 years) - All Subjects

Listing 16.2-17.2.1.1.2: Treatment-emergent Adverse Events (Group 2: 6 to < 12 years) - All Subjects

Listing 16.2-17.2.2.1.1: Treatment-emergent Study Drug Related Adverse Events (Group 1: 12 to <17 years) -All Subjects Listing 16.2-17.2.2.1.2: Treatment-emergent Study Drug Related Adverse Events (Group 2: 6 to < 12 years) -All Subjects Note to programmer: Replace "TREATMENT" with "SURGERY TYPE", followed by "Spine Surgery" or "Cardiac Surgery". Listing 16.2-17.3.1.1: All Serious Adverse Events (Group 1: 12 to <17 years) - All Subjects Listing 16.2-17.3.1.2: All Serious Adverse Events (Group 2: 6 to < 12 years) - All Subjects Note to programmer: Replace "TREATMENT" with "SURGERY TYPE", followed by "Spine Surgery" or "Cardiac Surgery". Listing 16.2-17.4.1.1.1: Treatment-emergent Serious Adverse Events (Group 1: 12 to <17 years) - All Subjects Listing 16.2-17.4.1.1.2: Treatment-emergent Serious Adverse Events (Group 2: 6 to < 12 years) - All Subjects Note to programmer: Replace "TREATMENT" with "SURGERY TYPE", followed by "Spine Surgery" or "Cardiac Surgerv". Listing 16.2-17.4.2.1.1: Treatment-emergent Study Drug Related Serious Adverse Events (Group 1: 12 to <17 years) - All Subjects Listing 16.2-17.4.2.1.2: Treatment-emergent Study Drug Related Serious Adverse Events (Group 2: 6 to < 12 years) - All Subjects **Note to programmer:** Replace "TREATMENT" with "SURGERY TYPE", followed by "Spine Surgery" or "Cardiac Surgery". Listing 16.2-17.5.1.1.1: Treatment-emergent Adverse Events of Special Interest, as Reported by Investigators (Group 1: 12 to <17 years) - All Subjects Listing 16.2-17.5.1.1.2: Treatment-emergent Adverse Events of Special Interest, as Reported by Investigators (Group 2: 6 to < 12 years) - All Subjects Note to programmer: Replace "TREATMENT" with "SURGERY TYPE", followed by "Spine Surgery" or "Cardiac Surgery". For these tables, use the CRF checkbox to identify AEs of Special Interest. Listing 16.2-17.5.2.1.1: Treatment-emergent Study Drug Related Adverse Events of Special Interest (Group 1: 12 to <17 years) - All Subjects Listing 16.2-17.5.2.1.2: Treatment-emergent Study Drug Related Adverse Events of Special Interest (Group 2: 6 to < 12 years) - All Subjects

Pacira Pharmaceuticals, Inc.	402-C-319
